6.3 Pharmacokinetics (this will come from the protocol pharmacologist)

6.4 Viral Load at Weeks 24 and 48:

Virologic outcomes, based on HIV-1 RNA (copies/ml), will be assessed at weeks 8, 12, 24 and 48. The criteria for success are: at least a 0.5 log₁₀ reduction in HIV-1 RNA (copies/ml) at week 8, at least a 1 log₁₀ reduction in HIV-1 RNA (copies/ml) at week 12 and either HIV-1RNA <400 copies/ml or at least a 2 log reduction in HIV-1 RNA at weeks 24 and 48.

At each of these time points the primary definition of virologic outcome will be calculated according to a Missing, Switch or Discontinuation = Failure (MSDF) algorithm – as codified by the FDA’s snapshot algorithm. Subjects will be classified as virologic failures if they have missing HIV-1 RNA data throughout the window surrounding the time point of interest.

In addition subjects will be classified as virologic failures at any of these time points if they meet any of the following conditions prior to that time point:

- a) Discontinuation of study treatment (except as allowed in protocol for Cohort IIIB subjects whose screening resistance data is not available at time of treatment initiation, but indicates lack of sensitivity to ETR when it becomes available);
- b) Change in background therapy not allowed in the protocol;
- c) Change in background ART substitutions permitted per protocol but prescribed while HIV-1 RNA \geq 400 copies/mL, unless the decision to switch is documented as being before or at the first on-treatment visit where HIV-1 RNA is assessed (Week 4).

6.5 Immunologic Response: CD4 Count and Percentages at Weeks 24 and 48:

Change from baseline to weeks 24 and 48 in CD4 count, CD4 percent and CD4/CD8 ratio will be bounded by 95% confidence intervals and presented both in the aggregate and by age cohort. In addition, the proportions of subjects exhibiting an absolute drop of >5% in CD4 percent from baseline to weeks 12, 24 and 48 will be presented, bounded by 95% confidence intervals. Subjects who meet any of the conditions (a) to (c) of Section 8.6321 or who have absolute drop of >5% in their CD4% will be considered as treatment failures in these analyses.

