6.5 Permitted Changes to the ARV Optimized Background Therapy During the Study

Any changes in background ARV therapy after initial optimization must be approved by the P1090 core protocol team. Unless the change is specifically permitted, subjects who have one or more new agents added to the optimized background CART regimen will be considered virologic failures.

The following changes to optimized background therapy are permitted during the study. However, the P1090 core protocol team requests that they be notified of any of these changes BEFORE they occur ([contact]).

- Subjects may discontinue a background ARV (if approved by the P1090 team) and remain on study and on study drug
- Formulation substitutions for NRTI class (substituting single agents for fixed dose combinations and vice versa of the same ARV, or switching from liquid to pill/capsule form) are allowed.
- Formulation substitutions for PI class (capsule to tablet or liquid, or vice versa) are permitted only after discussion with the P1090 core protocol team, including the pharmacologists. In certain cases, repeat PK evaluations may be requested
- Substitution within the NRTI or PI class, for reasons of toxicity or intolerance will be considered. If approved, the subject will remain on study drug, with the new PI, but considered as a virologic failure if the change occurs after the week 4 visit.

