8.3 Randomization and Stratification

There will be no randomization. Subjects will be enrolled into one of the three cohorts described in the “General Design Issues” section above.

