- a) Discontinuation of study treatment due to reasons other than AE or death and viral load was > 400 copies/mL at last available visit.
- b) Change in background therapy not allowed in the protocol.
- c) Change in background ART substitutions permitted per protocol unless the decision to switch is documented as being before or at the first on-treatment visit where HIV-1 RNA is assessed (Week 4).

Subjects who only discontinued a background ARV or who had formula substitutions (substituting single agents for fixed dose combinations and vice versa of the same ARV) in their OBT are not considered as having OBT changes and will not be analyzed as virologic failures. Otherwise, virologic success will be defined as having HIV-1 RNA ≤ 400 copies/mL by the last available HIV-1 RNA assessment while the subject is on-treatment within the visit of interest window. The proportions of subjects meeting the criteria for virologic success at each of these time points will be bounded by exact 95% confidence intervals, and will be presented both in the aggregate and broken down by age cohort.

Table 9 presents exact 95% confidence intervals around various potential rates of virologic success which might be observed in a total sample of 36 subjects or in subsamples of various sizes (N = 12, 24).

Table 9. Percent of Subjects Meeting Criterion for Virologic Success with Exact 95% Confidence Intervals

N	No. of Subjects (%) with Undetectable RNA	95% C.I.
12	1 (8%)	0.2% -- 38%
24	2 (8%)	1% -- 27%
36	4 (11%)	3% -- 26%
12	3 (25%)	5% -- 57%
24	6 (25%)	10% -- 47%
36	9 (25%)	12% -- 42%
12	6 (50%)	21% -- 79%
24	12 (50%)	29% -- 71%
36	18 (50%)	33% -- 67%
12	9 (75%)	43% -- 95%
24	18 (75%)	53% -- 90%
36	27 (75%)	58% -- 88%
12	11 (92%)	62% -- 99.8%
24	22 (92%)	73% -- 99%
36	33 (92%)	78% -- 98%

8.6322 CD4 Response

Change from baseline to weeks 24 and 48 in CD4 count, CD4 percent and CD4/CD8 ratio and percent will be bounded by 95% confidence intervals and presented both in the aggregate and by age cohort. In addition, the proportions of subjects exhibiting an absolute drop of > 5% in CD4 percent from baseline to weeks 12, 24 and 48 will be presented, bounded by 95% confidence intervals. Subjects who meet any of the conditions (a) to (c) of Section 8.6321 or who have absolute drop of > 5% in their CD4% will be considered as treatment failures in these analyses.

8.6323 HIV Drug Resistance

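### SAP 6.4 and Protocol 8.6321 define virologic failure differently, and SAP 6.5 cites the protocol's list, so the same child can be classed two ways

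*SAP*

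**What the plan says.** Both documents assess virologic outcome at Weeks 8, 12, 24 and 48 with a snapshot-type algorithm in which missing data, switches and discontinuations can count as failure. Each then lists conditions (a) to (c). Condition (b), a background change that is not allowed, is the same in both. The other two differ.

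**Condition (a), stopping etravirine.** Protocol 8.6321 fails "Discontinuation of study treatment due to reasons other than AE or death and viral load was" above 400 copies/mL at the last available visit. SAP 6.4 fails any discontinuation, "except as allowed in protocol for Cohort IIIB subjects whose screening resistance data is not available at time of treatment initiation" but later shows lack of sensitivity.

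**Condition (c), permitted switches.** Protocol 8.6321 fails "Change in background ART substitutions permitted per protocol unless the decision to switch is documented as being before or at the first on-treatment visit" with an RNA result (Week 4). Protocol 6.5 agrees for within-class changes: the child stays on study drug "but considered as a virologic failure if the change occurs after the week 4 visit". SAP 6.4 fails a "Change in background ART substitutions permitted per protocol but prescribed while HIV-1 RNA" is 400 or more, with the same Week 4 allowance.

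**Exemption.** Protocol 8.6321 adds that children who only dropped a background drug, or who had formulation swaps ("substituting single agents for fixed dose combinations and vice versa of the same ARV) in their OBT are not considered as having OBT changes"), are not failures. SAP 6.4 does not repeat this.

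**CD4.** SAP 6.5 counts as treatment failures the children who meet (a) to (c) of Section 8.6321, or whose CD4 percent falls by more than 5 points. The SAP has no Section 8.6321. The sentence also stands in Protocol 8.6322, where the number points to the protocol's own list.

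**The concern.** Virologic success and CD4 response are the key secondary results. A programmer who follows the SAP to the letter would apply one list to viral load and another to CD4, and a reader who recalculates from the protocol could get a different viral-load rate. The two lists err in opposite directions: the SAP is stricter on stopping and looser on switching while suppressed.

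The SAP's exception has no one to apply to. Protocol 8.3 says "Subjects will be enrolled into one of the three cohorts described in the" general design section, SAP 2 lists the same three, and neither has a Cohort IIIB. Table 6 of the protocol wants resistance results in hand before study drug in every cohort, and Appendix IC, footnote 15, repeats this for Cohort III genotyping. A rule that allows two answers for one child should be settled before the data are seen.

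**Working it through.** **1. The plan's own figures.** Clopper-Pearson 95% intervals reproduce all 15 rows of Protocol Table 9, for example 9/12 = 75% (42.8–94.5; stated 43–95) and 27/36 = 75% (57.8–87.9; stated 58–88). The point rests on wording and disputes no stated figure.

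**2. The two lists side by side, taking (a) and (c) alone.**

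| Case | Protocol 8.6321 | SAP 6.4 |
|---|---|---|
| Stop for AE or death, last RNA ≤ 400 | not failed | failed |
| Stop for AE or death, last RNA > 400 | not failed | failed |
| Stop for another reason, last RNA ≤ 400 | not failed | failed |
| Stop for another reason, last RNA > 400 | failed | failed |
| Switch by Week 4, RNA < 400 | not failed | not failed |
| Switch by Week 4, RNA ≥ 400 | not failed | not failed |
| Switch after Week 4, RNA < 400 | failed | not failed |
| Switch after Week 4, RNA ≥ 400 | failed | failed |

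Four of the eight cases disagree: three where the SAP is stricter, one where it is looser.

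**3. From condition to viral-load result.** Not every disagreement changes the reported rate. Protocol 8.6321 ends by requiring an on-treatment RNA at or below 400 within the window. A child who stops before the window opens has no such value, so is not a success under the protocol, and SAP (a) gives the same answer. Two groups remain:
- Stops after a qualifying on-treatment value already in the window. Example for Week 24 (SAP 7: days 141–196, target 169): RNA at or below 400 on day 156, stop for an AE on day 162. This is success under the protocol. It is failure under SAP (a) if the time point is taken as the target day.
- Permitted switches after Week 4 while suppressed: failure under the protocol, not under SAP (c).

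**4. Inside the SAP.** Taking the citation in 6.5 literally:
- A suppressed child switched within class at Week 16 is not failed in 6.4 but is a treatment failure in 6.5.
- A child who stops for an AE meets (a) in 6.4 but not (a) in 6.5, and fails there only through another condition or the CD4 drop.

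**5. Size per child.** 1/36 = 2.8 points; 1/12 = 8.3 points. Around an illustrative 75%:
- N=36: 26/36 = 72.2% (54.8–85.8) or 28/36 = 77.8% (60.8–89.9).
- N=12: 8/12 = 66.7% (34.9–90.1) or 10/12 = 83.3% (51.6–97.9).

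**6. What happens if protocol (a) is simply copied into the SAP.** Appendix ID schedules an RNA test 4 weeks (± 2 weeks) after stopping. A stop for an AE on day 135 puts it on day 135 + 28 = 163 (range 149–177), inside the Week 24 window. SAP 7's Follow-up row (after last dose + 1 = day 136) claims the same value, and no precedence is stated. The nominal test falls in the window for stops on days 113–140 (Week 24, from day 141) and 281–308 (Week 48, from day 309). SAP (a) as written blocks this off-drug success; protocol (a) alone would not.

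**The case against.** Several points on the other side stand.

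- **Regulatory scope.** The protocol introduces its algorithm as being for regulatory submissions, and SAP 1 excludes the sponsor's interim regulatory analyses, so two lists might serve two purposes. This explains part of the difference. It does not explain why the CD4 analysis, which carries no such limit, cites the protocol's section.
- **Copying slip.** The sentence in SAP 6.5 is the one in Protocol 8.6322, and the number may have come along unedited. If so, the conflict inside the SAP disappears and only the one with the protocol remains.
- **SAP (a) is defensible.** It suits an algorithm in which discontinuation means failure. The Cohort IIIB clause may suggest an older list, but the documents do not prove it, and nothing shows that the protocol's version of (a) must replace the SAP's.

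A reader might also infer more than the text supports:

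- That every AE stop changes the viral-load rate. Step 3 shows that most stops before a window are non-successes either way.
- That the SAP has two competing Week 24/48 criteria. It has one, below 400 or a 2 log fall, which apart from the strict inequality matches Protocol 8.22, the opening of Protocol 8.6321 and SAP 5. The competing sentence is in the protocol and may be regulatory only. The 2 log arm matters only for baselines above 400 × 100 = 40,000, and the inequality only for a value of exactly 400.
- That the SAP fails fixed-dose swaps made at 400 or more. Protocol 6.5 does list "Formulation substitutions for NRTI class (substituting single agents for fixed dose combinations and vice versa of the same ARV" among permitted changes, but Protocol 8.6321 says such swaps are not regimen changes, and the SAP's silence need not reverse that.

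**Conclusion.** The point holds in limited form. Conditions (a) and (c) differ between SAP 6.4 and Protocol 8.6321, the SAP carries an exception that cannot apply, and its CD4 section cites a list other than its own. Whether the SAP also contradicts itself depends on reading the 8.6321 citation literally.

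Each reclassified child moves the viral-load rate by 2.8 points at N=36 or 8.3 at N=12. The documents do not say how many children would be affected, and the net direction is unknown. As a rough guide to AE stops only, Protocol 1.32 reports permanent stops for AEs in PIANO in 2 of 41 children and 6 of 60 adolescents, so 8 of 101 overall. Assuming those rates, 36 × 2/41 = 1.8 to 36 × 8/101 = 2.9 children would stop, and only some would have a qualifying RNA in the window. PIANO enrolled ages 6 to 17, so this is an assumption.

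The outcome is secondary, single-arm and estimated without a test, so no trial conclusion turns on it. It should still be settled before database freeze.

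**What to change.** Before database freeze:

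1. Use one list of (a) to (c) for SAP 6.4 and 6.5, cite it by the SAP's own section number, and delete the Cohort IIIB exception.
2. Align (c) with Protocol 8.6321 and 6.5. Carry over the whole exemption (children who only dropped a background drug, and formulation substitutions), and state whether it covers the other formulation changes that Protocol 6.5 permits, such as liquid to pill or capsule to tablet.
3. Choose one rule for (a) and apply it in both analyses. Either keep the SAP's rule that any discontinuation is failure, or adopt protocol (a). If protocol (a) is adopted, also require an on-treatment RNA in the window for success, let the Follow-up row in SAP 7 override the week rows, and state how AE stops count for CD4.
4. Write 400 or below in SAP 6.4.
5. Keep 400 or below, or a 2 log fall, as the SAP's Week 24/48 criterion, and state whether the protocol's closing sentence (400 or below only) applies to regulatory submissions alone.

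The cost is SAP wording and programming. The reported rate may move slightly in either direction.

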6.6 HIV Drug Resistance

Correlations between baseline HIV genotypic and phenotypic drug resistance and any subsequent virologic failure will be evaluated. Subjects will be assessed for HIV genotypic and phenotypic drug resistance to the OBT and etravirine at screening, at the time of virologic failure (if this occurs) and at early discontinuation.

7 **Week Windows for Analyses:**

The week windows for all analyses will be as follows:

Study Day of Assessment	Assessment Window	Target Study Day of Window
-3 to 1	Week 0	1
2 to 42	Week 4	29
43 to 70	Week 8	57
71 to 98	Week 12	85
99 to 140	Week 16	113
141 to 196	Week 24	169
197 to 252	Week 32	225
253 to 308	Week 40	281
309 to 378	Week 48	337
379 to 462	Week 60	421
463 to 546	Week 72	505
547 to 630	Week 84	589
631 to 714	Week 96	673
715 to 798	Week 108	757
799 to 882	Week 120	841
883 to 966	Week 132	925
967 to 1050	Week 144	1009
1051 to 1134	Week 156	1093
1135 to 1218	Week 168	1177
1219 to 1302	Week 180	1261
1303 to 1386	Week 192	1345

1387 to 1470	Week 204	1429
1471 to 1554	Week 216	1513
Study Day of Assessment	Assessment Window	Target Study Day of Window
1555 to 1638	Week 228	1597
1639 to 1722	Week 240	1681
1723 to 1806	Week 252	1765
1807 to 1890	Week 264	1849
1891 to 1974	Week 276	1933
1975 to 2030	Week 288	2017
> (Study Day of last dose + 1)	Follow-up	Study Day of last dose + 14
